Subjects randomized to oral CHG will be provided verbal and written instruction on use of CHG oral rinse. Subjects will be asked to use CHG oral rinse twice daily for 7 days. Subjects will be educated to rinse their mouth and gargle with CHG oral rinse for 60 seconds twice a day. Subjects will be instructed to use a watch or other timing device (e.g., smartphone) to ensure that at least 60 seconds have elapses. Research staff will demonstrate the technique for all subjects using drinking water. All subjects randomized to the CHG arm will be provided a new soft bristle toothbrush to prevent recontamination of the oropharynx with *S. aureus* from a contaminated toothbrush. Subjects randomized to usual care will not be provided with any of the above. Regardless of treatment allocation, study staff will educate all subjects' parent/guardian, and subject (if of sufficient age) with the clinical significance of the results of their positive test for oropharyngeal

S. aureus colonization. More specifically, they will be educated that currently testing for *S. aureus* oropharyngeal colonization is considered experimental and that if the test is positive, the clinical significance is unclear. They will also be educated that tens of millions, perhaps over 100 million Americans are colonized in the throat with *S. aureus*, and the vast majority do not suffer consequences of having this bacteria reside in the throat. Upon request, subjects will be provided with a written copy of their results as well as a written description of the clinical significance of oropharyngeal colonization that they can share with their provider, if they wish. All subjects, regardless of treatment allocation, will be provided written and verbal information about *S. aureus* and skin infection prevention and recognition of early disease. These materials were developed for previous studies done by our group.¹⁸

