Participants will be asked to come to the research clinic 7 days after initiation of oral CHG, i.e., at the end of their treatment (Visit 2). A subsequent visit will occur at 28 days (Visit 3). The purpose of these visits is to ascertain oropharyngeal eradication of *S. aureus* both short term (primary study outcome) and longer term. Based on previous investigations conducted at our center(s), we estimate a 10% attrition rate.^{75,77,78,81,82} At Visit 2, participants will be swabbed the nares and oropharynx for the presence of *S. aureus* and to complete a follow-up survey about any recurrent infections, new medical history, or receipt of antibiotics. At Visit 3, participants will return to the research clinic to complete a follow-up survey. Study staff will also call all subjects remind them of their upcoming study appointments and at days 14 and 21 to address any questions the participant or their parent/guardian may have about the study. Adverse events will be measured at each scheduled and unscheduled (see below) follow-up visits. Adverse events will be measured using the Medical Dictionary for Regulatory Activities Terminology (MedDRA) version 14.0 or later terms.

Unscheduled visits

If participants or their parent/guardian experience potential adverse drug events that occur during the follow up period, subjects or their parent/guardian will be encouraged to contact study staff. If the event may be of clinical concern, the event will be referred to a study physician and the oral rinse discontinued, if applicable. If deemed necessary by the study physician or the subjects' primary physician, participants will be asked to return to the research clinic for evaluation by a study investigator.

Aim 1: Determine the efficacy of oropharyngeal decolonization among children suffering from CA-MRSA and other *S. aureus* skin infections

To determine if oropharyngeal *S. aureus* colonization can be eradicated, we will perform a prospective, double blind randomized controlled clinical trial of 0.12% oral chlorhexidine (CHG) oral rinse versus placebo for children age 5-17 with *S. aureus* oropharyngeal colonization. We hypothesize that 0.12% CHG rinse will

reduce oral *S. aureus* colonization better than placebo treatment. The findings from this Aim will provide “proof of principle” data on the ability of oral antiseptics to eradicate oropharyngeal *S. aureus* colonization in children.

Power and Sample Size

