Given this investigation is minimal risk, Data and Safety Monitoring (DSM) will be performed by the Investigative Team. DSM will be performed according to standards of The Eunice Kennedy Shriver National Institute of Child Health and Human Development (NICHD) Policy for Data & Safety Monitoring.⁹¹ These will include reviewing monthly summaries of the number of patients enrolled, age, ethnic and gender makeup, Number of patients retained in the study, number of dropout and lost to follow up, adverse events (AEs), and serious adverse events (SAEs) (See Aim 2, below for further details). Subjects that report treatment related adverse events will discontinue the oral rinse and come to the research clinic for an unscheduled visit.

Aim 2: Assess the safety, tolerability, and compliance of oropharyngeal decolonization among children and their caregivers. We will administer a detailed and systematic survey of side effects, tolerability and compliance of the oropharyngeal decolonization regimen to determine the effects, concerns, and usability of this regimen in children for both the child participants and their parents/caregivers. Findings will identify adverse effects and barriers to use to be considered when possibly administering this regimen in the future.

Data Analyses

Adverse events will be coded to a Medical Dictionary for Regulatory Activities Terminology (MedDRA) version 14.0 or later terms. Verbatim description and the MedDRA System Organ Class and Preferred Term for all adverse events will be contained in the subject data listings. A separate listing sorted

by MedDRA System Organ Class and Preferred Term will include all verbatim descriptions associated with the Preferred Terms.

Data for adverse events will be analyzed using the treatment-emergent signs and symptoms philosophy.

Treatment emergent signs and symptoms are defined as adverse events where:

- onset occurs during exposure to study medication or within 7 days after the last dose of study medication, having been absent prior to receiving study medication, or
- onset reoccurs during exposure to study medication or within 7 days after the last dose of study medication, having been present but stopping prior to receiving study medication, or
- worsening in severity occurs during exposure to study medication relative to the pre-treatment state, when the adverse event is continuous.

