All subjects who have consented will have the rapid *S. aureus* test performed with results shared with the subject's parent/guardian, the subject, and the clinician, if approved by the parent/guardian. Study staff will educate and the subject's parent/guardian, and subject (if of sufficient age), the clinical significance of the results, either positive or negative. More specifically, they will be educated that currently testing for *S. aureus* oropharyngeal colonization is considered experimental and that if the test is positive, the clinical significance is unclear. They will also be educated that tens of millions, perhaps over 100 million Americans are colonized in the throat with *S. aureus*, and the vast majority do not suffer consequences of having this bacteria live in the throat. Upon request, subjects will be provided with a written copy of their results as well as a written description of the clinical significance of oropharyngeal colonization that they can share with their provider, if they wish.

Subjects with a positive screening test will undergo 3 study visits total: baseline/enrollment visit (Visit 1), Day 7 (Visit 2), and Day 28 (Visit 3). Consenting subjects will have their anterior nares and oropharynx swabbed at Visits 1, 2, and 3. A survey will be administered at the initial visit and a follow-up survey will be administered at Visits 2, and 3. The survey administered at Visit 1 will collect information about demographics, medical history, and behavioral risk factors for skin and soft tissue infection and colonization. Subjects will be randomized to 0.12% CHG oral rinse or placebo use for 7 days. All subjects will receive educational materials regarding *S. aureus* and skin infections and their prevention. Those randomized to the intervention will receive additional verbal and written information on use of CHG oral rinse. The survey administered at Visit 2 will collect information about the adherence, tolerability, and adverse events during the intervention period. The survey administered at Visit 3 will collect information about (late) adverse events, changes in household dynamics and individual behavior (e.g., hygiene) that may affect results of Visit 3 nasal and oropharyngeal colonization studies.

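### No solicited adverse-event enquiry is planned between Day 7 and Day 28, although the treatment-emergent window runs to about Day 13-14 and a Day 14 call is already scheduled

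*Combined protocol and SAP*

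**What the plan says.** All references are to the combined protocol and SAP.

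- **Treatment course** (Baseline visit): "Subjects will be asked to use CHG oral rinse twice daily for 7 days".
- **Treatment-emergent definition** (Aim 2, Data Analyses): there are three routes. A new event qualifies if "onset occurs during exposure to study medication or within 7 days after the last dose of study medication". A recurring event qualifies if "onset reoccurs during exposure to study medication or within 7 days after the last dose of study medication". A continuing event qualifies if "worsening in severity occurs during exposure to study medication relative to the pre-treatment state". The first two carry a 7-day tail after treatment; the third does not.
- **Use of the definition** (Aim 2, Data Analyses): summary tables are restricted to treatment-emergent events. The by-subject listing takes every reported event.
- **Assessment points** (Follow-up visits): "Adverse events will be measured at each scheduled and unscheduled (see below) follow-up visits". The scheduled follow-up visits are on Day 7 (Visit 2) and Day 28 (Visit 3).
- **Survey content** (Human Subjects/Investigational New Drug): "The survey administered at Visit 2 will collect information about the adherence, tolerability, and adverse events during the intervention period". The Visit 3 survey asks about late adverse events.
- **Telephone calls** (Follow-up visits): apart from appointment reminders, staff call all subjects "at days 14 and 21 to address any questions the participant or their parent/guardian may have about the study". No adverse-event function is stated for these calls.
- **Passive routes:** families are encouraged to contact staff about possible drug reactions (Unscheduled visits). Subjects are told to report any adverse event and may phone staff to do so (Human Subjects). Those reporting treatment-related events attend an unscheduled visit (Data Analyses and Data and Safety Monitoring).

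**The concern.** The analysis definition and the data-collection schedule do not line up. The definition extends about a week beyond the end of treatment, yet nobody is scheduled to ask about adverse events in that week. The next solicited enquiry comes two weeks or more after the window has closed. Staff do speak to every family on about the day it closes, but the plan gives them nothing to ask.

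Onset date decides whether an event reaches the summary tables. If a family does not report a mild, short event when it happens, it may be forgotten by Day 28, or recalled with an onset on the wrong side of the boundary. Safety and tolerability make up Aim 2, and the plan compares adverse-event percentages between arms by chi-square or Fisher tests, so the completeness of this part of the window bears on a stated objective. It does not touch the primary outcome.

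**Working it through.** The plan gives no figure to reproduce here. The check is timeline arithmetic, with visits and calls taken on their nominal days.

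**Inputs.** Course of 7 days; tail of 7 days after the last dose; Visit 2 at Day 7; call at Day 14; Visit 3 at Day 28. The last dose, L, falls on Day 6 if the first day of use is Day 0, and on Day 7 if it is Day 1.

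**Step 1, end of window** = L + 7.
- L = 6: 6 + 7 = Day 13.
- L = 7: 7 + 7 = Day 14.

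**Step 2, part of the window after Visit 2** = (L + 7) − 7 = L days, that is 6 or 7 days. This is close to half of the window. A subject who stops early has a shorter gap: if the last dose is on Day 3, the window closes on Day 10 and 3 days fall after Visit 2.

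**Step 3, delay from onset to the next scheduled enquiry (Day 28).**
- Onset on Day 7: 28 − 7 = 21 days.
- Onset on the last day of the window: 28 − 13 = 15, or 28 − 14 = 14 days.
- Range: 14 to 21 days.

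**Step 4, the same delay if the Day 14 call asked.**
- Onset on Day 7: 14 − 7 = 7 days.
- Onset on the last day of the window: 14 − 13 = 1, or 14 − 14 = 0 days.
- Range: 0 to 7 days.

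**Step 5, which events are affected.** New-onset and recurring events have the tail, so they are affected. Worsening counts only during exposure, so it has no unassessed tail. Onsets during the course are asked about at Visit 2.

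**Step 6, consequence for the comparison.** Let pC and pP be the true proportions with post-treatment onsets in the chlorhexidine and placebo arms, and let s be the fraction captured, assumed equal in both arms. The observed difference is s·pC − s·pP = s(pC − pP). If pC = pP, nothing is diluted. If they differ, the absolute difference shrinks by the factor s and the ratio (s·pC)/(s·pP) = pC/pP is unchanged. The documents give no value for s, pC or pP, so no count of lost events can be derived.

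**Scale only.** With 60 randomized and 30 in the chlorhexidine arm, one subject counted or not counted moves an arm's incidence by 1/30 = 3.3 percentage points.

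**The case against.** The strongest reply is that the period is not unobserved. Families are encouraged to phone, subjects are told to report any adverse event, staff carry phones for this purpose, and unscheduled visits are assessment points. The Day 14 call is itself a conversation with the staff to whom events should be reported. This stands: a reader might infer that events in the second week are assessed solely by recall at Day 28, and the documents do not support that. What is absent is solicited enquiry. Passive reporting still depends on the family judging an event worth mentioning. For a mild event that is phoned in without leading to a visit, the plan names no point at which onset, stop date and severity are recorded.

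A reader might also infer that the gap biases the comparison toward chlorhexidine looking like placebo, because the known effects of the rinse (staining, calculus, altered taste) would be forgotten by Day 28. The documents do not support this either. Those are listed as effects of using the rinse, and onsets during use are solicited at Visit 2. Nothing says they begin after the last dose, or that the arms differ in post-treatment onsets. Ascertainment is the same in both arms of a double-blind trial.

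Finally, a misdated event is not lost: every reported event goes into the by-subject listing. Only its place in the summary tables is at risk, and mainly for onsets near the boundary.

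**Conclusion.** The point holds as a modest gap in ascertainment with a nearly free remedy. For a full course, 6 to 7 days of the treatment-emergent window have no solicited enquiry until Day 28, which is 14 to 21 days after onset. New-onset and recurring events that are mild, brief and not volunteered may be under-ascertained or misdated. To say that they will be would go beyond the documents, which support a risk and give no event rate from which to size it. Any dilution of a between-arm difference is conditional on a true difference in post-treatment onsets.

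This rests on a full 7-day course, contacts on their nominal days, and reading the call's stated purpose as its whole content. If staff in practice already ask about adverse events at Day 14, the gap lies in the text only, and the same amendment closes it. Sample size, significance level and the primary analysis are unaffected.

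**What to change.** In the Follow-up visits section, give the Day 14 call a short script, identical in both arms, that asks the Visit 2 adverse-event questions and records onset date, stop date and severity for each event. In the same section, add this call to the list of points at which adverse events are measured. Visit 3 would still pick up anything starting after the call.

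The longest delay from onset to a solicited enquiry, for onsets in the post-treatment part of the window, then falls from 21 days to 7. The cost is the script and a few extra minutes on a call already planned for every randomized subject, with no added visit. The change should be in place before enrolment, because onset dates that were never recorded cannot be recovered reliably. Scripting the Day 21 call in the same way is optional: the window has closed by then, so this point does not require it.

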Traditionally eradication efforts of *S. aureus* colonization have focused on removing colonization in the anterior nares (nose) and skin. A recent investigation by our group found that among persons with an *S. aureus* SSTI and their household members, the most common site of colonization of *S. aureus* on the human body is not the anterior nares, but the oropharynx (26% vs. 24%), with overlap of colonization far from universal. In fact, 50% of oropharyngeally colonized persons were not nasally colonized. Other investigations show a similar magnitude of *S. aureus* oropharyngeal colonization. There are mounting data that decolonization regimens that ignore the pharynx are not effective at preventing recurrent *S. aureus* SSTIs. However, prospective data on oropharyngeal decolonization of *S. aureus* in children are lacking.

We hypothesize that suboptimal *S. aureus* prevention efforts stem from previous inattention to eradication of *S. aureus* oropharyngeal colonization. To this end, we will conduct a clinical trial on eradication of oropharyngeal *S. aureus* colonization. Data from our "proof of principle" study will form the foundation of more comprehensive efforts to prevent recurrent *S. aureus* infections in children.

We will perform a prospective, double blind, randomized controlled clinical trial of 0.12% chlorhexidine (CHG) oral rinse versus placebo oral rinse for children age 5-17 with *S. aureus* oropharyngeal colonization. We hypothesize that, compared to placebo, 0.12% CHG rinse will reduce oral *S. aureus* colonization. We choose CHG given its wide availability, excellent safety profile, and low cost. We will enroll 240 children who have a history of *S. aureus* infection or SSTI in the prior year. Consenting subjects will be screened for *S. aureus* oropharyngeal colonization using a rapid molecular test. Subjects will be eligible if they have *S. aureus* oropharyngeal colonization during a screening visit, are able to gargle, and can be followed for 28 days. CHG oral rinse will be used twice daily for 7 days total.

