- Because trials on prevention of recurrent *S. aureus* infections have been disappointing, we will examine the efficacy of oropharyngeal *S. aureus* decolonization with 0.12% chlorhexidine gluconate (CHG) oral rinse, a widely available commercial product with an excellent safety profile.

Hypotheses

- Oral CHG rinse (0.12%) will be more effective than placebo at eradicating *S. aureus* oropharyngeal colonization after treatment completion.

Specific Aims

- To determine if CHG oral rinse can decolonize *S. aureus* oropharyngeal colonization better than placebo in children.

Study design

- Randomized, prospective, double-blind, placebo-controlled clinical trial of 0.12% CHG oral rinse vs. placebo oral rinse to decolonize the oropharynx among children.

Describe study population or sample material

- Subjects 5-17 years of age who have confirmed colonization of the oropharynx with *S. aureus* and who are able to gargle.

Sample size/power of primary endpoint

- The primary endpoint is eradication of *S. aureus* oropharyngeal colonization. To have 85% power to detect a 40% absolute difference in eradication between groups (10% for placebo and 50% for CHG), we will require 54 subjects total who complete the trial. We will need to screen potentially eligible children with rapid molecular tests for *S. aureus* oropharyngeal colonization to find eligible subjects. Estimating 25% of screened children will be eligible, and accounting for a 10% attrition rate, we will need to enroll 240 children for screening with the expectation that 60 will be eligible and participate and 54 will complete the clinical trial.

Assuming the project is successful, state the next step moving down the pathway to clinical applicability

- A randomized, prospective, multi-center, clinical trial of children of prevention of *S. aureus* skin infection that includes CHG oral rinses (in addition to body and nasal disinfectants) with a comparator group that will depend on standard of care at the time of development of the clinical trial protocol.

Hypothesis(es) and Aims (Do not exceed one page)

A. Hypothesis(es) to be Tested

Our primary hypothesis is 0.12% CHG oral rinse will be superior to placebo at eradicating *S. aureus* from the oropharynx of children age 5-17 colonized with *S. aureus* compared to placebo oral rinse.

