Figure 2. Timeline of Study Activities

[figure not shown]
Activities	Year 1	Year 2
Ramp-up of investigation, IRB submission, development of study protocol, analysis plan, and databases		
Recruitment/Enrollment of Subjects		
Follow-up of Subjects		
Whole Genome Sequencing of S. aureus and MRSA Isolates		
Data analysis and interpretation, manuscript preparation and submission, study close-out		

Enrollment of a cohort of pediatric patients with *S. aureus* skin and soft tissue infection

Enrollment

We will enroll 240 subjects with a history of SSTI in the Pediatric Emergency Department (PED) at Harbor-UCLA Medical Center. Subjects who meet the inclusion and exclusion criteria outlined below will undergo rapid screening for oropharyngeal *S. aureus* colonization. Assuming a 25% oropharyngeal colonization prevalence,¹⁸ 60 subjects will have oropharyngeal colonization with a *S. aureus* and be eligible for the trial's decolonization regimen (Figure 3).

Figure 3. Screening of Subjects for Enrollment

query PED physicians, and nursing staff about potentially interested patients (e.g., those with a history of SSTIs) whose parents/guardians are willing to discuss possible participation in a study. PED staff will also be in-serviced about the study and encouraged by our PED physician Co-Investigator to call study coordinators as needed. To complement these efforts, flyers will be placed in the PED advertising to medical staff to call or page study coordinators about potentially eligible patients. These strategies have been highly successfully at each of the sites for enrolling subjects with SSTIs in the PED for our previous investigations. Once an interested patient is identified, the study coordinator will complete the informed consent process in a private setting in the patient's parent/guardian preferred language (English or Spanish).

Inclusion and Exclusion criteria

For this investigation, we will use strict inclusion and exclusion criteria. Inclusion criteria will include:

- History of skin or soft tissue infection, as per patient report
- Age \geq 5 years and $<$ 18 years.
- Able to gargle (if needed, ability to gargle can be assessed at screening using water).
- Willing and able to undergo nares and oropharyngeal swabbing.
- Able to come to the research clinic for study follow-up visits for the study period.

Exclusion criteria for subjects will include:

- Suspected or confirmed infection requiring systemic antibiotics.

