Once a patient consents to study participation, study coordinators will obtain a specimen from the subject's nares, and oropharynx for both rapid testing and standard culture based testing. A research assistant will then process the swab for rapid molecular testing (GeneXpert MRSA/SA platform) to determine if the purulent fluid has MRSA, MSSA, or neither. The sensitivity and specificity of this FDA approved assay in the nares are 97 and 96%, respectively,⁶⁵ sensitivity for throat specimens is 75%-81% with a very high sensitivity of 98%.^{87,88} The specimen will be processed in the [name] Laboratory on the Harbor-UCLA Medical Center campus, which is a <5 minute walk from the PED. Rapid molecular testing results will be available within one hour and conveyed to the subject. Participants who are negative for *S. aureus* oropharyngeal colonization will be told they are not eligible for the intervention and discontinued from the study.

Participants who are positive for *S. aureus* oropharyngeal colonization will be allowed to participate in the trial and data collection will commence. Of note, participants who are rapid test positive for *S. aureus* and later using clinical microbiology lab testing with culture-based methods are found to be negative for *S. aureus* will not be included in the analysis, although given the very high sensitivity of the GeneXpert assay in throat specimens (98%), we think this is an unlikely event⁸⁷ and these events are built into our expected attrition rate (see below). For ethical purposes, all subjects, regardless of rapid testing results, will receive educational materials regarding optimal hygienic practices to reduce risk of transmission, basic education about *S. aureus*, SSTI, and recognition of warning signs of serious skin infections. These materials were developed for previous investigations and available in English and Spanish.

Based on previous investigations of patients with a history of skin infection from our group,¹⁸ we estimate 33% of children with a history of SSTIs will be positive for *S. aureus* (n=80, Figure 2). Assuming a 75% sensitivity of the GeneXpert assay, and 75% of those participants (n=60) will be positive at the oropharynx (see section on Power and Sample size, below). Study coordinators will complete the baseline visit for participants who are *S. aureus* positive on rapid molecular testing.

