Using an alpha of 0.05 and expected cure rates of 50% and 10% in the CHG and placebo arms respectively, 54 subjects (27 per group) would be needed for 85% power to detect a 40% absolute difference in cure ($p<0.05$) between groups. Correcting for a 10% attrition rate, 60 enrolled subjects would be needed. To identify 60 subjects with oropharyngeal colonization, and assuming 33% of patients who are high risk for *S. aureus* colonization will have oropharyngeal colonization, 240 subjects will need to be screened to obtain 80 patients that are oropharyngeally colonized with *S. aureus*. Of these, 75% (n=60) will have *S. aureus* detected by the GeneXpert rapid test and will undergo randomization.

Data Analyses and Data and Safety Monitoring

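### The 240-screen figure rests on inconsistent inputs: throat prevalence is 25% in Enrollment and 33% in Power and Sample Size, and no throat rate in the document reaches 33%

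*Combined protocol and SAP*

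**What the plan says.** The combined protocol and SAP derives the screening number in four places.

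- **Power and Sample Size (Aim 1):** "240 subjects will need to be screened to obtain 80 patients that are oropharyngeally colonized", using 33% throat colonization. The rapid test then detects 75% of the 80, so 60 are randomized. Allowing 10% attrition, 54 complete (27 per arm), for 85% power at 50% versus 10% eradication.
- **Enrollment:** "Assuming a 25% oropharyngeal colonization prevalence", so that 60 of the 240 are colonized and eligible. No sensitivity factor is applied.
- **Baseline visit:** "Based on previous investigations of patients with a history of skin infection from our group", "we estimate 33% of children with a history of SSTIs will be positive for" *S. aureus* (n=80). No body site is named. The 75% then appears both as assay sensitivity and as the share positive at the throat. This 33% and the Enrollment section's 25% cite the same reference.
- **Structured Abstract:** "Estimating 25% of screened children will be eligible", leading to 60 participants and 54 completers.

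On the status of the 240, the Enrollment section says "We will enroll 240 subjects with a history of SSTI" and the Scientific Abstract "We will enroll 240 children who have a history of" *S. aureus* infection or SSTI. The Human Subjects section describes 240 as the anticipated enrolment needed to randomize 60.

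The throat rates reported elsewhere are:

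- 26% in patients with SSTI and household members combined ("but the oropharynx (26% vs. 24%), with overlap of colonization far from universal" in the Scientific Abstract; repeated in Supportive Preliminary Data)
- 30% in household contacts and 31% in contacts of CA-MRSA cases (Background and Significance)
- 21% and 22% at baseline in the two arms of a trial in recently hospitalized adults (Supportive Preliminary Data)

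**The concern.** Out of the same 240 children, the number colonized in the throat cannot be both 60 and 80. Both sections end at 60 eligible, which hides the conflict: one reaches 60 with a lower prevalence and a perfect test, the other with a higher prevalence and a test that misses a quarter of carriers.

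The higher prevalence carries the calculation, and it lies above every throat rate the document reports. If the true rate is nearer those figures, 240 screens may not deliver 60 randomized children. The text does not say whether screening would then continue past 240.

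**Working it through.** **1. The plan's own figures reproduce.**

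- Screening: 240 x 1/3 = 80; 80 x 0.75 = 60; 60 x 0.9 = 54. With 33% exactly, 240 x 0.33 x 0.75 = 59.4.
- Sample size: the two-proportion formula at 50% versus 10%, two-sided alpha 0.05 and 85% power gives 22 per arm without and 27 per arm with continuity correction. Exact two-sided Fisher power at 27 per arm is 0.873.

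**2. What the 25% is.** 0.33 x 0.75 = 0.2475. The Structured Abstract's 25% eligible is therefore the product of the two factors in Power and Sample Size. If 25% really were a prevalence, the true-positive yield would be 240 x 0.25 x 0.75 = 45.0, or 48.6 at 81% sensitivity, not 60.

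**3. Yield at the reported rates.** Inputs are throat prevalence of 26%, 30% or 31% and throat sensitivity of 75% or 81% (the range in Baseline visit).

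- True positives (TP) = 240 x prevalence x sensitivity.
- False positives (FP) = 240 x (1 - prevalence) x 0.02. This assumes that the second throat figure in Baseline visit, 98%, printed there as a sensitivity, is a specificity.
- Completers are 0.9 x TP if false positives are a loss on top of the 10% attrition. They are 0.9 x (TP + FP) if false positives sit inside it, as Baseline visit says.
- Screens needed for 60 true positives = 60 / (prevalence x sensitivity).

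Paired values are for 75% / 81% sensitivity.

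| Prevalence | TP | 0.9 x TP | FP | TP + FP | 0.9 x (TP + FP) | Screens for 60 TP |
|---|---|---|---|---|---|---|
| 26% | 46.8 / 50.5 | 42.1 / 45.5 | 3.6 | 50.4 / 54.1 | 45.3 / 48.7 | 308 / 285 |
| 30% | 54.0 / 58.3 | 48.6 / 52.5 | 3.4 | 57.4 / 61.7 | 51.6 / 55.5 | 267 / 247 |
| 31% | 55.8 / 60.3 | 50.2 / 54.2 | 3.3 | 59.1 / 63.6 | 53.2 / 57.2 | 258 / 239 |

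The adult-trial baselines would give 240 x 0.21 x 0.75 = 37.8 to 240 x 0.22 x 0.81 = 42.8 true positives. They are left out of the range because that population is furthest from the trial's.

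**4. Power.** Exact two-sided Fisher test (the test named in Data Analyses), 50% versus 10%, summed over all binomial outcomes.

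- Equal arms, by number per arm: 21, 0.759; 22, 0.786; 24, 0.834; 25, 0.833; 26, 0.855; 27, 0.873; 28, 0.891.
- Nearly equal arms: 42 completers split 20/22 or 22/20 give 0.811-0.816; 45 split 22/23 give 0.825 (CHG arm larger) to 0.852 (CHG arm smaller).
- At 30-31%, with 49-54 completers in equal arms, power is about 83-87%; counting false positives inside attrition it is about 83-89%.
- At 26%, equal arms give about 76-79%, or 79-83% with false positives inside attrition. Slightly unequal arms bring it to about 81-85%. The most favourable case, 49 completers split 24 CHG and 25 placebo, gives 0.870.

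**The case against.** The strongest defence is that nothing is miscalculated. Read with 25% as the net yield, every section arrives at the same 60, and the Enrollment section merely carries a wrong label. That stands, and so do the 54 and 60. A reader might infer that the sample size is wrong or that the trial is underpowered; the document does not support this.

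A reader might also infer that 33% is false. It is not shown to be. The Baseline visit section attributes it to the group's own earlier patients, in a source not available here, and the comparison rates come from adults or mixed-age groups, two of them from household contacts. Sampling error matters too: 31% of 268 contacts has a Wilson 95% interval of about 26-37%, which includes 33%. The 30% is also compatible if it refers to the 812 contacts in Supportive Preliminary Data (about 27.0-33.3%). Only the pooled 26% is clearly lower.

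Nor is 47-60 the number randomized. It counts true positives. On the specificity reading about 50-64 children would be randomized, because rapid-positive, culture-negative children enter the trial and are later dropped from analysis.

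Finally, the 76% figure partly reflects the discreteness of Fisher's test, since the same 42 completers in arms of 20 and 22 give about 81%.

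The plan also leans towards 60 as the goal: Power and Sample Size and Human Subjects both derive 240 from it, enrolment is reviewed monthly, and no sentence caps screening at 240. But no sentence says that screening continues either, and two sections state 240 as the number that will be enrolled.

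**Conclusion.** The inconsistency is real and minor. The Enrollment section most likely labels the net eligible fraction as a prevalence, Baseline visit garbles the same chain, and the 240 rests on a 33% throat prevalence that no rate in the document reaches. That 33% is unsupported, not disproved, for children with a prior SSTI.

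Only the screening yield is affected. At 26-31% and 75-81%, 240 screens give about 47-60 true positives and 42-54 analysable completers. With 98% taken as specificity and false positives inside the 10% attrition, the figures are about 50-64 randomized and 45-57 completers. The stated 85% power roughly holds at 30-31%. A material loss arises only near 26%, where power is about 76-85% depending on the arm split and on how false positives are counted.

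These figures assume 10% attrition, 50% versus 10% eradication, a two-sided 0.05 test, and that screening stops at 240.

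**What to change.** 1. Use one chain, throat prevalence x throat sensitivity, in Enrollment, Baseline visit, and Power and Sample Size. Label 25% as the net eligible fraction in the Structured Abstract and in Enrollment. State whether the 98% is a specificity.
2. Give the source of the 33%, with the population and body site it refers to, or replace it with the reported range.
3. Then choose one of two options:
   - **(a)** State that 60 randomized is the target and that 240 is the expected, not the fixed, number of screens (about 240-310 at 26-31%). Change the sentences in the Scientific Abstract and Enrollment that commit to enrolling 240.
   - **(b)** Keep 240 screens and restate expected yield, completers and power as the ranges above, saying whether false positives are counted.

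The cost is a wording amendment. Option (a) may need up to about 70 extra swab screens at the reported 26-31% (308 - 240 = 68). Option (b) needs no extra children but prints a less favourable lower end for power. The primary test, the effect size and the 54-completer target stay as they are.
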